## **Revision history**

See below for descriptions of changes. Refer to the header stamp for the date of approval of the most recent version.

Version	Study Protocol Version	Version Description and reason for change(s)	
1.0	1.0	First issue	
1.01	1.03	Addition of trial registration numbers	

## 1 Background & rationale

The H1 Implant is a cementless, ceramic-on-ceramic hip resurfacing arthroplasty (HRA) device (Figure 1). The H1 Implant that has so far been used exclusively in a Clinical Investigation sponsored by Embody Orthopaedic Limited (Embody) (ISRCTN91554748, NCT03326804). The H1 Implant is set to receive CE marking in early 2024. This statistical analysis plan (SAP) relates to a randomised control trial (RCT) being sponsored by Embody to ascertain whether the composite clinical success of the H1 Implant is non-inferior to cementless total hip replacement (THR): "The ACTIVE Trial". The RCT is being managed by Imperial College London, acting as a contract research organisation (CRO).

[figure not shown]

Figure 1. Schematic drawings of the H1 femoral head (left) and acetabular cup (right)

## 2 Specific objectives and hypotheses

#### 2.1 Research hypothesis

The H1 Implant is non-inferior to cementless total hip replacement (THR), in terms of composite clinical success (CCS) at 24 months post-op.

## 2.2 Study objectives

The primary objective of this trial is to determine whether the H1 Implant is non-inferior to cementless THR in terms of CCS.

The key secondary objective is to determine whether the H1 Implant is superior compared to cementless THR in terms of physical activity and patient report outcome measures (PROMs).

Other secondary objectives are to compare the H1 Implant and cementless THR with respect to:

- Safety, through collection of all procedure and device related adverse events
- Noise generation, through patient survey.

## 3 Trial methods

## 3.1 Trial design

The ACTIVE Trial is designed as a randomised (1:1), controlled, assessor- and patient-blinded multicentre non-inferiority trial with two parallel groups and a primary endpoint of composite clinical success 24 months after surgery. The parallel groups will be:

- 1) Experimental: The H1 Implant;
- 2) ACTIVE comparator: cementless total hip replacement (THR).

## 3.2 Randomisation and blinding

Randomisation will be performed using variable block randomisation with block sizes of 4, 6 and 8, with a 1:1 allocation to the 2 groups, with stratification across sites. This will ensure approximately equal numbers across groups and approximately the same number per group at each site (to control for differences in the trial population because of environmental, social and demographic factors), while allowing different total numbers at each site. It will also ensure that at any given time, the numbers in each group will be approximately equal, allowing the interim analyses to take place. The randomisation will be managed by the CRO via an electronic data capture (EDC) system, which uses a validated randomisation algorithm (Castor EDC). Once a patient has been consented, they will be assigned to a treatment group according to the pre-determined order inside the block. Stratification by site is recommended for multi-centre studies. The patients, clinical assessors and data analysts will be blinded to the intervention each patient has received for the 24 month post-operative period. The surgeon, operating theatre team, radiographic analysts and CRO cannot be blinded but will not be involved in the care of the patient after the intervention unless the patient requires revision surgery.

## 3.3 Sample size

The sample size was calculated on the basis of the research hypothesis. Using pilot data from two sources, the CCS rates for cementless THR and the H1 Implant were estimated to be 91%3\* and 92.7%, respectively. With a non-inferiority margin of 8% and setting the probability of a type I error to 5% and power to 80% and using the following formula:

$$n = \left(\frac{z_{1-\alpha} + z_{1-\beta}}{P_{H1} - P_{THR} - \delta}\right)^2 \left(P_{H1}(1 - P_{H1}) + P_{THR}(1 - P_{THR})\right)$$

where:

n = required sample size  $P_{H1}$  = probability of success for H1  $P_{THR}$  = probability of success for THR  $\alpha$  = probability of a type I error  $\beta$  = probability of a type II error  $\delta$  = non-inferiority margin

<sup>\*This CCS for the cementless total hip was calculated from the publication referenced, but excluded intra-operative ceramic liner fractures because these have been practically eliminated with modern day ceramic (BIOLOX®*delta*) and do not occur with polyethylene cups. The control in the RCT will be cementless BIOLOX®*delta*-on-BIOLOX®*delta* or cementless BIOLOX®*delta*-on-PE THRs.

z = is the cumulative distribution function of a standardised normal deviate

The required sample size is 93 per group. Allowing for drop-outs, this gives a sample size of 100 per treatment arm, therefore a total of 200 patients will be recruited to the study. Assuming the cementless THR group goes on to match this pilot data of 91% success, 90% of H1 patients would be required to demonstrate composite clinical success to be non-inferior to the THR patients, with the margin of 8%.

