#### 3.5.2 Planned adjustment of significance level due to interim analysis

Because multiple statistical comparisons will be performed (interim analyses and final analysis), the risk of false positive (type I) error will be inflated. Therefore a group sequential  $\alpha$ -spending function shall be used, calculated using the O'Brien-Fleming method, with two-sided symmetric bounds. This gives p-values of 0.00005, 0.0039, 0.0184 and 0.0412 at the three interim analyses and the final analysis, respectively.

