## 4 Statistical principles

### 4.1 P-values and confidence intervals

#### 4.1.1 Level of statistical significance

All applicable statistical tests will be either 1-sided or 2-sided depending on the outcome and will be performed using a 5% significance level.

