#### 4.1.4 Confidence intervals to be reported

All confidence intervals presented will be 95% and two-sided.

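### The 93 per group does not follow from the printed inputs (the formula gives 99), and the sizing ignores the 0.0412 final level, whose one-sided meaning is not fixed

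*SAP*

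**What the plan says.** Section 3.3 takes success rates of 91% for cementless THR and 92.7% for H1 from pilot data. It sets the design values as "With a non-inferiority margin of 8% and setting the probability of a type I error to 5% and power to 80" per cent. The formula uses z at 1 - alpha, so the sizing is one-sided. Its denominator subtracts delta, which is defined as the non-inferiority margin. The result is "The required sample size is 93 per group", raised to 100 per arm for drop-outs. If THR reaches 91%, the section adds, "90% of H1 patients would be required to demonstrate composite clinical success to be non-inferior to the THR patients".

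Section 3.5.1 plans three interim analyses that include the primary endpoint. Section 3.5.2 applies O'Brien-Fleming bounds, two-sided and symmetric: "This gives p-values of 0.00005, 0.0039, 0.0184 and 0.0412 at the three interim analyses and the final analysis, respectively".

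Section 4.1.1 says: "All applicable statistical tests will be either 1-sided or 2-sided depending on the outcome and will be performed using a 5% significance level". Section 4.1.2.2 refers back to 3.5.2 for the interim adjustment. Section 4.1.4 says: "All confidence intervals presented will be 95% and two-sided". Table 1 names Blackwelder's test for the primary outcome but gives neither level nor side.

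**The concern.** Two things do not fit. The stated sample size is not what the formula returns from the rates printed beside it. And the sizing spends the full one-sided 5% at a single look, although the same plan reduces the final level to 0.0412 because of the interim analyses.

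The second point is the more serious. A bound of 0.0412 from a two-sided symmetric design puts 0.0206 on each side, while a non-inferiority test uses one side only. The SAP does not say which of the two figures the primary p-value is compared with. At stake are the power the trial can claim and, near the margin, the non-inferiority verdict.

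**Working it through.** **Inputs.** P_THR = 0.91, P_H1 = 0.927, margin 0.08, alpha = 0.05 (one-sided), power 0.80, n = 93 and 100 per arm (all section 3.3); final level 0.0412 (section 3.5.2).

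**1. Sample size.** Variance sum = 0.927 × 0.073 + 0.91 × 0.09 = 0.149571. (z_0.95 + z_0.80)² = (1.6449 + 0.8416)² = 6.183.

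- With delta = -0.08 the denominator is 0.927 - 0.91 + 0.08 = 0.097, and n = 6.183 × 0.149571 / 0.097² = 98.3, so 99.
- With delta = +0.08 in the printed formula the denominator is -0.063, and n = 233. The plan evidently did not use this.
- With P_THR = 0.906 the variance sum is 0.152835, the denominator 0.101, and n = 92.6, so 93.

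Other standard variants do not give 93: pooled variance 99, Farrington-Manning 110, continuity correction 118, one-sided 2.5% 125, zero true difference 145. The stated figure is thus reproduced only with a THR rate near 90.6%, which would print as 91%.

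**2. Power at the final level.** Power = Phi(0.097/SE - z), with SE = sqrt(0.149571/n). The ratio 0.097/SE is 2.419 at n = 93 and 2.508 at n = 100.

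| One-sided level | z | n = 93 | n = 100 |
|---|---|---|---|
| 0.05 (as sized) | 1.645 | 78.1% | 80.6% |
| 0.0412 | 1.737 | 75.2% | 78.0% |
| 0.0206 | 2.0415 | 64.7% | 68.0% |

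For 80% power the formula needs 105.7 (106) per group at 0.0412 and 132.1 (133) at 0.0206. Simulating the Wald test with binomial counts gives 75.6% and 66.8% at n = 93, and 78.9% and 68.9% at n = 100. Counting earlier boundary crossings, under assumed equally spaced looks, adds about 1 point (76.4% and 66.1% at 93; 79.1% and 69.3% at 100).

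**3. Sensitivity to the THR rate.** If 90.6% lies behind the 93, the variance sum 0.152835 and distance 0.101 give ratios of 2.491 (n = 93) and 2.584 (n = 100). Power is then 77.5% or 67.4% with 93 evaluable, and 80.1% or 70.6% with 100 (0.0412 or 0.0206). Only the combination of one-sided 0.0412 and no drop-out reaches 80%.

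**4. Test and reported interval.** A two-sided 95% interval corresponds to one-sided 0.025, which is neither 0.0412 nor 0.0206. Two examples with 100 per arm:

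- 90 v 90 successes: SE = sqrt(0.18/100) = 0.0424. The lower limit is -7.4 points at one-sided 0.0412 (non-inferior) but -8.3 for the 95% interval (crosses -8).
- 91 v 91 successes: SE = sqrt(0.1638/100) = 0.0405. The lower limit is -7.9 for the 95% interval (clear of -8) but -8.3 at one-sided 0.0206 (not shown).

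**5. The H1 success threshold.** With THR at 91%, the H1 rate at which the lower limit equals -8 is:

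| One-sided level | n = 93 | n = 100 |
|---|---|---|
| 0.05 | 90.06% | 89.8% |
| 0.0412 | 90.4% | 90.2% |
| 0.0206 | 91.5% | 91.2% |

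Against 91 of 100 for THR, H1 therefore needs 90 of 100 at one-sided 5%, 91 at 0.0412 and 92 at 0.0206.

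**The case against.** The THR rate is printed as a whole per cent and was derived from a cited source with exclusions, so an unrounded 90.6% may well lie behind the 93. At one-sided 5% the consequence is small: 78.1% power at 93 and 80.6% at 100. This stands, which is why the point is that 93 cannot be reproduced from what is printed, and why stating the unrounded rate would settle it.

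Three stronger readings are tempting, and the document does not support them.

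- A reader might infer that the 90% figure for H1 is also wrong. It is not: at one-sided 5% the threshold is 89.8% to 90.06%. It only needs restating if the final level differs.
- A reader might infer that 5% in section 4.1.1 contradicts 0.0412 in section 3.5.2. An overall 5% with a smaller final nominal level is ordinary group-sequential design, and section 4.1.2.2 makes the link.
- A reader might infer that the trial needs 233 per group. That figure arises only from entering the margin as +8%; it is a matter of sign notation.

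It can also be said that section 4.1.4 is a reporting convention and that Blackwelder's test decides. That is fair, since the SAP nowhere makes the 95% interval the decision rule. It does not remove the risk that the published interval and the test point in different directions, nor does it say which level the test uses.

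**Conclusion.** The point holds in this form. On the printed inputs the required size is 99 per group, not 93, so 100 per arm leaves about 1% for drop-out rather than the 7% that 93 implies. The 80% power does not hold at the plan's own final level: it is 75% or 65% with 93 evaluable per arm and 78% or 68% with 100, according to whether the one-sided test uses 0.0412 or 0.0206. Most of that spread comes from the unresolved side. If 0.0412 is meant one-sided, the shortfall is about 2 to 5 points; if 0.0206 is meant, it is 12 to 15.

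These figures rest on the SAP's rates and margin, the normal approximation in its formula, and power at the final look only. An unrounded THR rate of 90.6% would raise them by roughly 2 to 3 points.

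**What to change.** In section 3.3, write the denominator with +delta, or define delta as -8%. Replace 93 by 99 and note that 100 per arm then leaves about 1% for drop-out; or keep 93 and state the unrounded THR rate that gives it.

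In sections 3.5.2 and 4.1, state one one-sided level for the final primary test, 0.0412 or 0.0206. Report the matching two-sided interval for the difference in CCS rates: 1 - 2 × 0.0412 = 91.76%, or 1 - 2 × 0.0206 = 95.88%. Declare non-inferiority if its lower limit is above -8%, and except this interval from the general 95% rule in section 4.1.4.

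Restate the achieved power at that level for 93 and 100 evaluable per arm. Restate the H1 threshold as a count against 91 of 100 for THR: 91 of 100 at 0.0412, or 92 of 100 at 0.0206.

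The cost is SAP wording and a less favourable stated power. No increase in enrolment is asked for.

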## 3.4 Framework

The study protocol states that the key secondary objective is to determine whether the H1 Implant is significantly different compared to cementless THR in terms of physical activity (measured via pervasive activity monitoring and physical performance assessment) and PROMs (the University of California at Los Angeles (UCLA) Activity Score and the Hip Outcome Score (HOS)). Therefore, the key secondary outcomes will be tested for significant differences rather than non-inferiority as for the primary outcome.

For the pervasive physical activity monitoring, with 100 patients in each group (determined by the primary outcome) and with THR patients expected to achieve a daily average of approximately 258 minutes of low, moderate and vigorous activity at the 12 months post-op timepoint, the H1 patients will have to achieve 287 minutes to demonstrate a significant difference (using the using the standard deviation of 100 minutes for the general population). If the H1 patients reach 338 minutes (thereby achieving maximum mortality risk reduction compared to the referent), significant difference will be demonstrated with >99% power.

In addition, periods of "bouted" MVPA are of interest as there is some evidence that, below a certain amount of MVPA per day, if a greater percentage of MVPA is conducted in 10-minute bouts, there is a greater risk reduction in overall mortality. With 100 patients in each group, H1 patients would have to achieve 60 minutes of 10-minute bouted MPVA per day to demonstrate a significant difference (90% power) compared to the approximately 48 minutes (SD 42 minutes) of 10-minute bouted MVPA per day estimated to be achieved by THR patients at the 1 year post-op timepoint.

The other secondary outcomes (safety and results of the noise assessment) will just be reported for both groups, no statistical analysis will take place.

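### The 90% power claimed for 60 v 48 minutes of bouted MVPA is wrong: with SD 42 and 100 per arm, power is about 50%

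*SAP*

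**What the plan says.** Section 3.4 of the SAP gives two planning figures for the activity monitor, both with 100 patients per arm.

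- **Bouted MVPA.** "H1 patients would have to achieve 60 minutes of 10-minute bouted MPVA per day to demonstrate a significant difference (90% power"). The comparator is "approximately 48 minutes (SD 42 minutes) of 10-minute bouted MVPA per day estimated to be achieved by THR patients" at one year.
- **Total activity.** Against 258 minutes for THR and an SD of 100, "the H1 patients will have to achieve 287 minutes to demonstrate a significant difference". No power is attached to this figure. A separate figure of 338 minutes is given with power above 99%.

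The significance level comes from two other places. Section 4.1.1 says: "All applicable statistical tests will be either 1-sided or 2-sided depending on the outcome and will be performed using a 5% significance level". Section 3.5.2 describes sequential bounds "calculated using the O'Brien-Fleming method, with two-sided symmetric bounds", and adds: "This gives p-values of 0.00005, 0.0039, 0.0184 and 0.0412 at the three interim analyses and the final analysis, respectively". Table 1 plans a Student's t, Welch's t or Wilcoxon rank-sum test for the activity outcomes and states the hypothesis as H1 being better. Section 6.2 rules out baseline adjustment.

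**The concern.** The mean, SD and number per arm stand in one sentence, so the power can be checked directly. A difference of 12 minutes is only 0.286 SD (12/42). With 100 per arm that is too small for 90% power in a two-sample comparison.

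Physical activity is part of the key secondary objective and is formally tested. A reader of the SAP would conclude that a true gain of 12 minutes a day would be missed one time in ten. On the SAP's own inputs it would be missed about one time in two. A non-significant result could then be read as good evidence against a 12-minute benefit that the trial had only an even chance of showing.

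**Working it through.** **Inputs.** From section 3.4: 100 per arm, THR mean 48, H1 mean 60, SD 42. Only one SD is given, so I assume it applies to both arms. From section 4.1.1: nominal level 5%, sidedness open. From section 3.5.2: 0.0412 at the final analysis, two-sided bounds.

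**Step 1: standard error and standardised difference.**

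SE = SD x sqrt(2/n) = 42 x sqrt(2/100) = 5.940 minutes

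(60 - 48)/5.940 = 2.020

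**Step 2: power.** Power = Phi(2.020 - z), where z is the critical value. With 93 per arm, SE = 42 x sqrt(2/93) = 6.159 and the ratio is 1.948.

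| Test | z | Power, 100 per arm | Power, 93 per arm |
|---|---|---|---|
| Two-sided 0.05 | 1.960 | 52.4% | 49.5% |
| Two-sided 0.0412 | 2.0415 | 49.2% | 46.3% |
| One-sided 0.05 | 1.645 | 64.6% | 61.9% |
| One-sided 0.0412 | 1.737 | 61.2% | 58.4% |

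For 100 per arm the noncentral t gives 52.0% and 48.7% for the two-sided rows. A simulation of 40,000 trials gives 51.7% and 48.3%. For the Wilcoxon test with normal data (efficiency 0.955), two-sided 0.05 gives about 51%.

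**Step 3: can 90% be reproduced?** Not from the stated design. The nearest set-ups are a one-sample test that treats 48 as a known constant (SE = 42/10 = 4.2) and 200 per arm (SE = 42 x sqrt(2/200) = 4.2). Each gives Phi(12/4.2 - 1.645) = 88.7% one-sided and 81.5% two-sided. Neither matches section 3.4.

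**Step 4: where 60 probably comes from.** The smallest significant difference is z x SE:

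- two-sided 0.0412: 2.0415 x 5.940 = 12.13, an H1 mean of 60.1
- two-sided 0.05: 1.960 x 5.940 = 11.64, an H1 mean of 59.6

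The total-activity figure follows the same pattern: SE = 100 x sqrt(2/100) = 14.14, and 258 + 2.0415 x 14.14 = 286.9, stated as 287. The 338-minute figure also reproduces: 80/14.14 = 5.66 SE, power above 99.9%. Of the figures in this section, only the 90% fails.

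**Step 5: what 90% power would take.** The required difference is (z + 1.2816) x SE:

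- two-sided 0.05: 3.2415 x 5.940 = 19.3, an H1 mean of 67.3
- two-sided 0.0412: 3.3231 x 5.940 = 19.7, an H1 mean of 67.7

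To keep 12 minutes at two-sided 0.05, n per arm = 2 x (3.2415 x 42/12)^2 = 257.4, so 258. Alternatively the SD would have to be 12/(3.2415 x sqrt(2/100)) = 26.2.

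**Step 6: Hochberg, as a lower bound.** Section 4.1.2.1 applies the Hochberg procedure to the tested secondary endpoints. Counting six from Table 1 (two activity measures, two performance tests, HOS, UCLA) is my assumption. At the strictest step, 0.0412/6 = 0.0069, z = 2.704 and power is Phi(2.020 - 2.704) = 25%.

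**The case against.** Several points can be made in the SAP's favour.

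- **Sidedness is not settled.** Section 4.1.1 allows one-sided tests and Table 1 words the hypothesis directionally. This stands: about 50% is the two-sided figure, and a one-sided 5% test gives 65%. The two-sided reading is the more natural one, since section 3.4 speaks of differences and section 3.5.2 sets two-sided bounds. Neither reading gives 90%.
- **The threshold explanation is inferred.** The SAP shows no derivation. The match for both 60 and 287 at two-sided 0.0412 makes the explanation likely, but the error stands without it.
- **The 287-minute figure is not wrong.** Read as a threshold it is correct, and no power is claimed for it. Relabelling it is a matter of clarity.
- **Skewed data and a rank test could change the power.** The SAP makes no such assumption. Under an assumed gamma distribution with mean 48 and SD 42, simulated Wilcoxon power at two-sided 0.05 was 36% for a scale effect and 78% for a pure shift. Both are below 90%.
- **The 93 and the Hochberg 25% are not forecasts.** Section 3.3 derives 93 for the primary outcome. The number with valid wear under section 6.1 may differ. Because Hochberg is a step-up procedure, 25% is a worst case.
- **The figure drives no decision.** Section 3.4 says the primary outcome fixes the number of patients. That limits the damage, but does not make the statement true.

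**Conclusion.** The concern holds. The SAP's own inputs give 49% to 52% power for a two-sided test and at most 65% for a one-sided 5% t-test, against the 90% stated. Nothing elsewhere in the SAP corrects this. The calculation assumes a common SD of 42, 100 analysed patients per arm and approximate normality. Loss of patients, invalid wear and the Hochberg adjustment would lower the power further.

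The error lies in the 90% label alone. It leaves the sample size and the primary analysis untouched, but it must be corrected because it misstates the type II risk of a formally tested key secondary endpoint.

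**What to change.** In section 3.4, replace the bouted-MVPA statement with one to this effect: with 100 per arm, SD 42 in both arms and a two-sided level of 0.0412, a true H1 mean of about 68 minutes against 48 would give 90% power; 60 minutes is roughly the significance threshold if the THR mean is 48, and a true mean of 60 would give about 50% power.

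For clarity, describe 287 minutes as a threshold too (power about 50%).

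State the level and sidedness behind each figure. If a one-sided 5% test is meant, the mean for 90% power is 48 + (1.645 + 1.2816) x 5.940 = 65.4 minutes.

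Repeat the figures for a smaller analysed number, labelled as an assumption. With 93 per arm at two-sided 0.0412:

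- MVPA threshold: 48 + 2.0415 x 6.159 = 60.6 minutes
- MVPA mean for 90% power: 48 + 3.3231 x 6.159 = 68.5 minutes
- Total-activity threshold: 258 + 2.0415 x 100 x sqrt(2/93) = 287.9 minutes

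Add that these figures do not allow for the Hochberg adjustment.

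The cost is a few sentences and a less favourable figure. Enrolment, tests and data collection do not change.

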## 3.5 Statistical interim analyses and stopping guidance

#### 3.5.1 Interim analyses

Three formal statistical interim analyses are planned on the primary and key secondary endpoints. These interim analyses are planned to take place when at least half the number of patients recruited for the final analysis have reached the 6 month, 12 month and 24 month post-operative time points (i.e. 50 H1 patients and 50 cementless THR patients have reached those time points, the CCS has been calculated and they have completed 2 weeks of activity monitoring).

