#### 3.5.3 Details of guidelines for stopping the trial early

Both the experimental arm (the H1 Implant) and the active comparator arm (cementless THR) are CE marked devices with proven safety and efficacy and by the time the first interim analysis is carried out,

most of the patients will have received their intervention. Therefore, the statistical results from the interim analyses alone will not be used to stop the trial early. However, if the interim analyses are cause for concern, safety information, as measured by adverse events and adverse device effects, will be closely assessed by the CRO and the sponsor to determine whether it can be justified to continue follow-up of the patients in the study.

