## **3.6** Timing of final analysis

The final analysis and preparation of the final report for the H1 Implant versus cementless THR comparison is planned to take place when all 200 patients have reached the 24 month post-operative time point and data for the primary and key secondary endpoints have been received. This is anticipated to be in June 2026.

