## 6 Analysis

## 6.1 Outcome definitions

The primary outcome is "composite clinical success". This is a binary outcome measure. Patients are deemed to have achieved CCS if they meet all of the following criteria at the 24 month timepoint:

- Modified Harris Hip Score  $\geq$ 80.
- No revision or pending revision.
- Acetabular radiolucencies: not in all zones.
- Femoral radiolucencies: not in all zones.
- Absence of subsidence/migration of the acetabular or femoral component >5mm with clinical findings.
- Absence of serious adverse device effect (SADE).

The secondary outcomes are:

- Total activity count (AC), calculated as the total time spent in non-sleep and non-sedentary activity (in minutes per week) and minutes (in bouts of at least 10 minutes) of moderate to vigorous physical activity (MVPA) achieved during a week, as measured by the GENEActiv activity tracker over a period of 14 days. Patients will be asked to wear the GENEActiv for the full 14 days, but some non-wear is expected, so for the individual patient's data to be valid, they must wear the device for at least 2 weekdays and 2 weekend-days, for a minimum of 2/3 of their waking hours on each of those days. Total weekly AC and MVPA will be calculated: [5× mean daily weekday AC/MVPA time + 2× mean daily weekend AC/MVPA time], to standardise across all patients no matter what their wear-time, as long as it meets the minimum requirements.
- Physical performance assessment. This will take the form of 2 assessments (30-second chair to stand (CTS) test and stair climb test (SCT)) recommended by Osteoarthritis Research Society International (OARSI) pre-operatively and at each post-operative time point.
- The UCLA Activity Score. This is a patient reported outcome measure (PROM) and takes the form of a self-administered questionnaire. The patient will score a mark between 1 and 10 pre-operatively (historical activity level), pre-operatively (current activity level) and at each post-operative time point (current activity level).
- Hip Outcome Score (HOS). This is a PROM and takes the form of a self-administered questionnaire focussing on activities of daily living and sports/exercise. The patient will score a mark between 0 and 100 pre-operatively and at each post-operative time point.

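### The interim p-value bounds assume four equally spaced looks at one accumulating statistic, but only the third interim and the final analysis test 24-month CCS; the bounds, their sidedness and the no-stopping rule need reconciling

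*SAP*

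**What the plan says.** - **Looks (SAP 3.5.1).** "Three formal statistical interim analyses are planned on the primary and key secondary endpoints". They occur "when at least half the number of patients recruited for the final analysis have reached the 6 month, 12 month and 24 month" post-operative visits, spelled out as "50 H1 patients and 50 cementless THR patients have reached those time points".
- **Bounds (SAP 3.5.2).** An alpha-spending function is "calculated using the O'Brien-Fleming method, with two-sided symmetric bounds". "This gives p-values of 0.00005, 0.0039, 0.0184 and 0.0412 at the three interim analyses and the final analysis", respectively. No information fractions are given.
- **Use of the looks (SAP 3.5.3).** "the statistical results from the interim analyses alone will not be used to stop the trial early". A worrying result leads to a closer safety assessment by the CRO and sponsor. The section does not say whether crossing a bound supports a claim.
- **Final analysis (SAP 3.6).** It is "planned to take place when all 200 patients have reached the 24 month post-operative time point".
- **Primary endpoint (SAP 6.1).** "Patients are deemed to have achieved CCS if they meet all of the following criteria at the 24 month timepoint".
- **Level.** The sample-size formula in SAP 3.3 uses the one-sided normal quantile at 5% and makes no allowance for interim looks. SAP 4.1.1 gives a 5% level for all tests, one- or two-sided by outcome. SAP 4.1.2.2 refers back to the adjusted p-values.

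**The concern.** Group-sequential bounds control error for a stated set of looks at one accumulating statistic. Here the number of patients stays at about 50 per arm over the three interims and the visit changes instead. For 24-month CCS the schedule amounts to two looks, at about 50% and 100% of the information, while the bounds are those of a four-look design.

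What is at stake is the threshold that decides non-inferiority. If an interim can support a claim, the third-look threshold is much looser than O'Brien-Fleming would allow at that point. If it cannot, the final analysis is held to 0.0412 for no return. The sidedness is also open: the bounds are two-sided and the sample size is one-sided, so an analyst cannot tell which level applies to the primary test.

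**Working it through.** **Inputs.** Bounds from SAP 3.5.2; 50 per arm per interim from 3.5.1; 100 per arm at the end from 3.6; CCS rates of 91% (THR) and 92.7% (H1), margin 8%, one-sided 5%, and 93 required and 100 recruited per arm from 3.3.

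**1. The plan's own bounds.** O'Brien-Fleming with K equally spaced looks has z_k = C·√(K/k), so z_k·√(k/K) should be constant. With K = 4:

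| Look | SAP p (two-sided) | z | z·√(k/4) | Exact 5% bound (C = 2.024) |
|---|---|---|---|---|
| 1 | 0.00005 | 4.056 | 2.028 | 0.00005 |
| 2 | 0.0039 | 2.886 | 2.041 | 0.0042 |
| 3 | 0.0184 | 2.357 | 2.042 | 0.0194 |
| Final | 0.0412 | 2.042 | 2.042 | 0.0429 |

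The fourth column is constant apart from rounding of the first p-value, so the equal-spacing form is clear. The values are not exact for 5%: at 25, 50, 75 and 100% information they spend 4.79%.

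**2. Actual timing for 24-month CCS.** Look 3 has 50 of 100 per arm, a fraction of 0.5; the final has 1.0. The two statistics correlate at √0.5 = 0.707. O'Brien-Fleming bounds for two looks at 50% and 100%:

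- two-sided 5%: C = 1.977, bounds 0.0052 and 0.0480;
- one-sided 5%: C = 1.678, bounds 0.0088 and 0.0467.

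The ratio 0.0184 / 0.0052 is about 3.5. Measured against the two-sided pair, look 3 is too lax and the final too strict.

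**3. If an interim crossing can support a claim.** Error spent under the null by 0.0184 at look 3 and 0.0412 at the final:

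| Information at look 3 | p-values read as two-sided | p-values read as one-sided |
|---|---|---|
| 50% | 5.18% | 5.05% |
| 55% | 5.09% | 4.96% |
| 60% | 5.00% | 4.88% |
| 75% | 4.69% | 4.59% |

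The 6- and 12-month looks were added by simulation (4 million draws). The SAP gives no correlation between the three interim statistics, so a common value of 0 to 0.9 was assumed. With look 3 at 50%, the total is 5.2 to 5.5% (two-sided reading) or 5.1 to 5.4% (one-sided reading).

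**4. If no interim supports a claim.** Power = Φ(0.097/SE − z), where 0.097 = 0.927 − 0.91 + 0.08 and SE = √[(0.927×0.073 + 0.91×0.09)/n]. SE is 0.03867 at n = 100 and 0.04010 at n = 93, so 0.097/SE is 2.508 and 2.419.

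| Final level | One-sided alpha | z | Power, 100 per arm | Power, 93 per arm |
|---|---|---|---|---|
| 0.05 one-sided | 0.05 | 1.645 | 80.6% | 78.1% |
| 0.0412 one-sided | 0.0412 | 1.737 | 78.0% | 75.2% |
| 0.05 two-sided | 0.025 | 1.960 | 70.8% | 67.7% |
| 0.0412 two-sided | 0.0206 | 2.042 | 68.0% | 64.7% |

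The cut from 0.05 to 0.0412 costs just under 3 points on either reading. Going from one-sided 5% to two-sided 5% costs about 10 points more.

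**The case against.** The strongest reply is that little harm follows.

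- **Error rate.** A reader might infer that the trial's 5% error rate is broken. The SAP does not support that as a flat statement. No section says that crossing an interim bound supports a claim, and 3.5.3 says interim results alone stop nothing. Even if claims were made, the excess is a fraction of a percentage point. The 5.18% counts both tails; if the bounds are two-sided, error in the non-inferiority direction from looks 3 and 4 is 2.6% (2.6 to 2.8% with the earlier looks), about half of a one-sided 5%. This stands and limits the point.
- **Timing.** Half is a minimum. For the look-3 and final pair the excess is gone by 60% information. This stands, but 3.5.1 spells out 50 + 50 and no larger fraction is planned.
- **Both harms together.** A reader might infer a lax interim bound and a wasted final level at once. They are alternatives: if a crossing can support a claim, the alpha is being used; if not, the look-3 bound does nothing.
- **Early looks.** It is tempting to say that the 6- and 12-month looks carry no information on the primary endpoint. That is too absolute. All outcomes are measured at each visit, and early failures, such as revisions, may persist to 24 months. What holds is that these looks do not test the 24-month outcome.
- **Key secondary endpoints.** These are also part of each interim, and SAP 3.4 works its activity calculations at 12 months. A 12-month look may matter for them, so a fix framed only around CCS would be incomplete. This stands.

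None of this reconciles the bounds with the looks, or settles which level applies at the end.

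**Conclusion.** The point holds in limited form. The bounds do not match the planned looks, and the SAP does not say what a crossing means or whether 0.0412 is one- or two-sided for the primary test.

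- **If claims are possible:** the look-3 bound is about 3.5 times the correctly timed two-sided one, but overall error rises only to about 5.1 to 5.5%. This assumes look 3 at 50% information and, for the range, the assumed correlations.
- **If they are not, the more natural reading of 3.5.3:** the adjustment only costs power. At 100 per arm it takes one-sided power from just above the planned 80% to 78.0%; a two-sided reading gives 68.0%. These figures rest on the SAP's own rates and margin and on an unpooled normal approximation. At 93 per arm power is 78.1% even without adjustment, so that part of the shortfall is not due to the bounds.

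A final level that is too strict makes the trial conservative; it does not make its conclusion invalid. The matter should still be corrected because it sets the primary decision threshold.

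**What to change.** **Preferred.** State in SAP 3.5 that no efficacy or non-inferiority claim will be made at any interim. Delete the adjusted p-values, and the cross-reference in 4.1.2.2. Test the final analysis at the full level, naming the sidedness used for the sample size in 3.3.

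**Alternative.** Keep one formal interim, on 24-month CCS. Say what a crossing would mean, and compute the bounds from the information fraction actually reached and the chosen sidedness. At 50% and 100% these are 0.0052 and 0.0480 (two-sided 5%) or 0.0088 and 0.0467 (one-sided 5%). Make the 6- and 12-month CCS looks descriptive.

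If the alternative is chosen and a formal 12-month analysis of the activity endpoints is wanted, set its level separately and tie it to the Hochberg procedure in 4.1.2.1.

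**Cost.** SAP wording only; no extra patients or visits. The sponsor gives up formal claims from the early looks, and under the preferred option from all three interims.
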